7.5 SECONDARY ENDPOINT

7.5.1 Key secondary endpoint

This section is not applicable as no key secondary endpoint has been specified.

7.5.2 Secondary endpoints

7.5.2.1 Secondary efficacy endpoints

The analysis of CRP, FCP and FLFwill be performed as defined in Section 7.3.2 of the CTP and will be based on the SAF.

The CRP, FCP and FLF will be descriptively summarized by visit as continuous variables. For each marker the absolute value and percent change from baseline will be analysed per treatment group via

• Mean, standard deviation, median, Q1, Q3, normalized IQR (0.7413*IQR), minimum, maximum, gMean

- Error bars for the median with Q1 being the lower end and Q3 the upper end of the bars of the respective outcome variable will be calculated for each time point. This information will be displayed graphically in conjunction with the median.
- Line plots presenting individual values of the respective outcome variable over time. Beside the individual patient lines also a median line will be depicted in all plots for a better visual interpretation.

In plots with absolute values reference lines indicating LLOQ and ULOQ may be included. In addition lower and upper limit of the normal range, if a normal range is available, will be presented.

The analysis of secondary efficacy endpoints will be performed as defined in Section 7.3.2 of the CTP and will be based on the FAS.

Total clincal remission at Week 12 will be assessed based on the proportion of patients with Total Mayo score ≤ 2 points, and all subscores ≤ 1 point (cf. Section 9.1.1). The proportion of patients with total clinical remission will be summarized descriptively by visit, presenting patient frequencies and proportions together with exact 95% Wilson score confidence intervals.

Additional displays of the patient frequencies and percentages for the individual total Mayo scores (resp. partial MCS), as well as for each of the four subscore (SFS, RBS, PGA and mESS; cf. Section 9.1.1) will also be produced. Furthermore line plots will be produced presenting Mayo score (resp. the Mayo subscores SFS, RBS, PGA and mESS) over time.

 TSAP for BI Trial No: 1368-0004
 Page 35 of 48

 Proprietary confidential information © 2019 Boehringer Ingelheim International GmbH or one or more of its affiliated companies

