7.3.2 Secondary endpoint analyses

The efficacy endpoints, such as percent change in CRP, will be evaluated descriptively, along with exact 95% confidence intervals, if feasible. Additionally the original as well as change from baseline values for all time points from baseline up to Week 12 will be presented. If the data appears to be very skewed then a log transformation and a summary statistic on the log scale will also be presented. Summary plots will also be produced if necessary.

The binary efficacy endpoint patient with clinical remission based on Mayo score at Week 12 will be described using patient frequencies and percentages. Exact 95% confidence intervals will additionally be provided for the proportion of patients, if feasible. Furthermore shift tables from baseline up to Week 12 will be produced for the Mayo score.

Analysis of safety and tolerability is described in Section 7.3.4.

Page 62 of 82

Proprietary confidential information © 2019 Boehringer Ingelheim International GmbH or one or more of its affiliated companies

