4. CHANGES IN THE PLANNED ANALYSIS OF THE STUDY

The following changes of endpoints (based on Mayo score) were implemented to be consistent across trials.

The following renamings were conducted:

- The secondary endpoint clinical remission (Mayo Score ≤2 with all subscores ≤1) will be labelled as *total clinical remission*
- The further endpoint Modified clinical remission (Mayo Score ≤2 AND (A) rectal bleeding subscore (RBS) = 0, (B) modified endoscopic subscore ≤1; and (C) stool frequency subscore = 0 or =1 and drop ≥ 1 from baseline) will be labelled as *clinical remission*

See Section 9.1 for details on deriving the efficacy endpoint scores at each visit.

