7. PLANNED ANALYSIS

The format of the listings and tables will follow the BI standards "Standards for Reporting of Clinical Trials and Project Summaries" (10).

A separate DMC SAP which describes the analyses required for assessment by the DMC will be produced and handled by the DMC.

The individual values of all patients will be listed. Listings will generally be sorted by country, centre number, patient number and visit (if visit is applicable in the respective listing). AE listings will be sorted by treatment (see Section 7.8.1 below for details). The listings will be contained in Appendix 16.2 (SDL) of the CTR.

The following standard descriptive statistical parameters will be displayed in summary tables of continuous variables:

Ν	number of non-missing observations
Mean	arithmetic mean
SD	standard deviation
Min	minimum
Q1	lower quartile
Median	median
Q3	upper quartile
Max	maximum

For plasma concentrations and some biomarkers, the following descriptive statistics will additionally be calculated:

CV	arithmetic coefficient of variation
gMean	geometric mean
gCV	geometric coefficient of variation

Statistical parameters will be displayed to a defined number of decimal places as specified in the BI standards "Standards for Reporting of Clinical Trials and Project Summaries" (10).

Tabulations of frequencies for categorical data will include all possible categories and will display the number of observations in a category as well as the percentage (%) relative to the respective treatment. Percentages will be rounded to one decimal place. The category missing will be displayed if and only if there actually are missing values. Percentages will be based on all patients in the respective patient set whether they have non-missing values or not.

Note that for the analysis of all data in this trial, the primary approach is to report only those data that fall within the on-treatment period. However, for selected displays of endpoints presented by-visit, additional ouputs which include both on- and off-treatment data will also be produced.

Disposition of the patient population participating in the trial will be summarised for the ES by presentation of the frequency of patients screened, entered, screened but not entered, treated, entered but not treated, who completed planned visit at Week 12, who completed all

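### SAP 7.5.2.1 calls a Wilson interval exact, asks for a geometric mean of percent change, and names an analysis set for three markers that conflicts with Table 6.3:1

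*SAP*

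**What the plan says.** **Remission interval.** SAP 7.5.2.1 summarises total clinical remission by visit, "presenting patient frequencies and proportions together with exact 95% Wilson score confidence intervals". Protocol 7.3.2 says "Exact 95% confidence intervals will additionally be provided for the proportion of patients, if feasible" and names no method. SAP Section 4, where departures from the protocol belong, opens with "The following changes of endpoints (based on Mayo score) were implemented to be consistent across trials" and in its published text lists only renamings of Mayo endpoints.

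**Marker statistics.** For CRP, faecal calprotectin (FCP) and faecal lactoferrin (FLF), SAP 7.5.2.1 says "For each marker the absolute value and percent change from baseline will be analysed per treatment group via" and then gives a single list: "Mean, standard deviation, median, Q1, Q3, normalized IQR (0.7413*IQR), minimum, maximum, gMean". SAP Section 7 introduces the geometric mean in general terms: "For plasma concentrations and some biomarkers, the following descriptive statistics will additionally be calculated". Protocol 7.3.2 makes log-scale summaries conditional: "If the data appears to be very skewed then a log transformation and a summary statistic on the log scale will also be presented".

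**Analysis set.** SAP 7.5.2.1 says "The analysis of CRP, FCP and FLFwill be performed as defined in Section 7.3.2 of the CTP and will be based on the SAF". SAP 5.2.2.1 lists the same three markers as secondary efficacy endpoints. A later sentence of 7.5.2.1 puts secondary efficacy endpoints on the FAS, and Table 6.3:1 assigns the secondary inflammatory endpoints to the FAS with the observed-cases (OC) approach.

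**The concern.** The words *exact* and *Wilson score* cannot both be true of one interval. An exact binomial interval guarantees at least 95% coverage, and a Wilson interval does not. A reader of the report would credit the remission interval with a guarantee it lacks.

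A geometric mean needs positive values. Percent change is zero or negative for every patient whose marker stays level or falls, and a fall is what an effective anti-inflammatory drug should produce. Followed literally, the cell is blank. If a programmer dropped the non-positive values, it would describe only the patients whose marker rose.

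The analysis set for three secondary endpoints depends on which sentence or table is read.

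**Working it through.** The documents give no interval or coverage figure to reproduce. The inputs are n = 10 (protocol 7.7), up to 4 replacements and so at most n = 14 (same section), and a 95% level.

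**1. Interval.** With z = 1.96, p = x/n and d = 1 + z²/n, the Wilson limits are

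(p + z²/2n)/d ± (z/d)·√(p(1−p)/n + z²/4n²).

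For x = 3, n = 10: d = 1.384, centre 0.3555, half-width 0.2477, so 10.8% to 60.3%. The Clopper-Pearson limits are the 2.5% quantile of Beta(x, n−x+1) and the 97.5% quantile of Beta(x+1, n−x), taking 0 as the lower limit when x = 0.

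| Remitters of 10 | Wilson | Clopper-Pearson |
|---|---|---|
| 0 | 0–27.8% | 0–30.8% |
| 1 | 1.8–40.4% | 0.3–44.5% |
| 2 | 5.7–51.0% | 2.5–55.6% |
| 3 | 10.8–60.3% | 6.7–65.2% |

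Over all x, the largest difference in a limit is 5.0 points at n = 10 and 3.8 points at n = 14.

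Coverage at a true rate p is the sum of binomial probabilities over those x whose interval contains p. Evaluated at 200,000 true rates between 0 and 1:

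| n | Method | Mean | Minimum | Share of true rates with coverage below 90% |
|---|---|---|---|---|
| 10 | Wilson | 95.4% | 83.5% (p near 1.8%) | 1.9% |
| 10 | Clopper-Pearson | 98.4% | 96.1% | 0 |
| 14 | Wilson | 95.4% | 83.6% | 1.3% |
| 14 | Clopper-Pearson | 98.0% | 95.5% | 0 |

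Wilson is close to nominal on average, but it is not exact.

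**2. Geometric mean of percent change.** It exists for the whole group only if every patient's marker rises. If each patient independently fails to rise with probability q (assumed), the chance that it can be computed is (1−q)ⁿ:

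| q | n = 10 | n = 14 |
|---|---|---|
| 50% | 0.1% | below 0.1% |
| 20% | 10.7% | 4.4% |
| 10% | 34.9% | 22.9% |
| 5% | 59.9% | 48.8% |

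An invented example shows what dropping non-positive changes would do. Take ratios to baseline of 0.2, 0.35, 0.5, 0.6, 0.7, 0.8, 0.9, 1.0, 1.2 and 1.6. Only two percent changes are positive, +20 and +60, and their geometric mean is √(20×60) = +34.6%. The median percent change is −25%. The geometric mean ratio, back-transformed as 100×(exp(mean log ratio) − 1), is −32.3%.

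A simulation of 200,000 trials of 10 patients, with log-normal ratios of median 0.5 and log-SD 0.5, 1.0 or 1.5 (all assumed), shows the same pattern. Among trials with at least one rise, the median value printed would be +18.3%, +55.5% or +113.2%. The median number of contributing patients is 1, 2 or 3. No patient rises in 42.2%, 6.1% or 2.0% of trials.

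**3. Analysis set.**

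| Place in SAP | Set for CRP, FCP, FLF |
|---|---|
| 7.5.2.1, sentence naming the markers | SAF |
| 7.5.2.1, later sentence on secondary efficacy endpoints, read with 5.2.2.1 | FAS |
| Table 6.3:1, secondary inflammatory endpoints | FAS, OC |

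Under SAP 6.3, the FAS drops patients without a baseline and a post-baseline value for any efficacy or biomarker endpoint, and patients with rescue use from Visit 1b up to the first dose. Percent change needs both values in either set, so the sets differ for it mainly through that early rescue use. The documents give no count. SAP 6.6.2 and Table 6.3:1 both give OC for efficacy data, so no conflict over rescue handling is claimed.

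**The case against.** **Interval.** The SAP names one computable method, and only an adjective is wrong. The protocol names no method, adds a feasibility clause, and in 7.2 says only that intervals may be presented. Choosing the method is the SAP's job. It stands that Wilson is defensible and that its worst coverage is confined to extreme true rates. It does not rescue the label. An exact binomial interval is always feasible with 10 patients, so the feasibility clause does not explain the change.

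**Geometric mean.** The mean, median, quartiles, range and plots remain valid, and the geometric mean suits the absolute values. The natural failure is a blank cell; a misleading number requires a programming choice that the documents do not mention. All of this stands. The simulated values show what that choice would do and do not predict what will be reported.

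**Analysis set.** SAP 6.3 allows the SAF for certain biomarkers, and the history table says version 3.0 changed biomarker analyses, so the SAF may be what was meant. The sentence naming the three markers could also be read as overriding the general one. The published text is incomplete here: there is no visible 6.6.5. These points leave the intended set open, but Table 6.3:1 still contradicts 7.5.2.1.

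**Conclusion.** The concern holds on all three counts, and its weight is minor. The interval is mislabelled, by at most 5.0 points in any limit at n = 10, and the departure from protocol 7.3.2 is unrecorded in the published text. The geometric mean of percent change is undefined as soon as one patient does not rise, and this needs no assumption. How often that happens depends on the assumed q. The figures for dropped values depend further on that programming choice and on the assumed log-normal ratios. The SAF/FAS point is an inconsistency of probably small numerical effect, and the documents do not settle which set was intended. Everything is confined to descriptive secondary summaries: no hypothesis is tested, protocol 7.2 treats intervals as interval estimates only, and the primary endpoint is unaffected.

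**What to change.** 1. In SAP 7.5.2.1, either specify exact 95% Clopper-Pearson intervals, or delete the word *exact*, keep Wilson, and record the departure from protocol 7.3.2 in SAP Section 4. Clopper-Pearson keeps the protocol's intent but is wider: at 3 of 10, 58.6 points against 49.5. Wilson costs one line in Section 4.
2. Restrict the geometric mean to absolute values. Where very skewed data trigger the log-scale summary of protocol 7.3.2, report change as the geometric mean ratio to baseline, back-transformed to percent change.
3. Give one analysis set for CRP, FCP and FLF, either by changing SAF to FAS in 7.5.2.1 or by correcting Table 6.3:1 and the conflicting FAS sentence in 7.5.2.1.

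Together these take a few words of SAP text and a few lines of code, with no new data.

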7.7 EXTENT OF EXPOSURE

The number of subjects who received a dose of trial drug will be tabulated. The duration of infusion [in minutes], the amount of treatment received (actual and weight based), as well as the volume infused [% of planned] will be listed.

7.8 SAFETY ANALYSIS

All safety analyses will be performed based on the SAF and following BI standards. No hypothesis testing is planned.

7.8.1 Adverse events

AEs will be coded with the most recent version of MedDRA.

The analyses of AEs will be descriptive in nature. All analyses of AEs will be based on the number of patients with AEs and not on the number of AEs. System organ classes (if applicable) will be sorted according to the standard sort order specified by the EMA, preferred terms (if applicable) will be sorted by total frequency (within system organ class).

For analysis, multiple AE occurrence data on the eCRF will be collapsed into one event provided that all of the following applies:

- All AE attributes are identical (lower level term, intensity, action taken, therapy required, seriousness, reason for seriousness, relationship, outcome, AESI)
- The occurrences were time-overlapping or time-adjacent (time-adjacency of two occurrences is given if the start date of the second, later occurrence is the same or one day later than the end date of the first occurrence)

For further details on summarization of AE data, please refer to "Analysis and Presentation of Adverse Event Data from Clinical Trials" (7) and "Handling of missing and incomplete AE dates" (4).

The analysis of AEs will be based on the concept of treatment emergent AEs. This means that all AEs will be assigned to the screening phase, on-treatment period or off-treatment period (i.e. follow-up) as defined in Section 6.1. Since only the start date of an AE is collected (without start time), any AE occurrence on the same day as first BI 655130 administration will be assigned to the on-treatment phase.

An overall summary of AEs will be presented. This overall summary will include summary statistics for the class of other significant AEs (sponsor definition based on ICH E3) according to ICH E3 (9) and for the class of AESIs.

The investigator had to classify on the eCRF whether an observed AE was an AESI or not.

The following is considered an AESI (cf. CTP section 5.3.5.1):

- Infusion reactions including anaphylactic reaction
- Cytokine release syndrome
- Opportunistic and mycobacterium tuberculosis infections
- Hepatic injury

The investigator identified AESI will be captured from the eCRF and reported as "Investigator reported AESI" table. In addition, user defined adverse event concepts (UDAEC) identified through specific search criteria will be reported separately (cf. Table 7.8.1:1).

Adverse event of special interest	Categories	
Infusion/Systemic hypersensitivity reactions including anaphylactic reactions	Narrow SMQ "Anaphylactic reaction" Narrow SMQ "Angioedema" Narrow SMQ "Hypersensitivity"	
Severe infections (according to RCTC grading)	SOC Infections and infestations of at least severe RCTC grade, by HLGT	
Opportunistic and mycobacterium tuberculosis infections	BIcMQ "Infections": Narrow sub-search 8 "Opportunistic infections including Tuberculosis related terms"	
Tuberculosis related terms	BIcMQ "Infections": Narrow sub-search 8.2 "Tuberculosis related terms" HLT "Tuberculosis infections"	
Malignant tumours	(SMQ "Malignancies" – not for display) (Sub-SMQ "Malignant or unspecified tumours" – not for display) Narrow Sub-SMQ "Malignant tumours" Sub-SMQ "Haematological malignant tumours" Sub-SMQ "Non-Haematological malignant tumours"	

Table 7.8.1: 1 Project MEDDRA search criteria for User Defined Adverse Event Concepts

Based on the specification provided in ICH E3 (9), the sponsor has defined AEs which are to be classified as 'other significant'. For the current trial, these will include those non-serious AEs which were reported with 'action taken = Drug withdrawn' or 'action taken = Dose reduced'.

The frequency of patients with AEs will be summarised by treatment, primary system organ class and preferred term. AEs which were considered by the investigator to be drug related will be summarised separately. Separate tables will also be provided for patients with SAEs, drug related SAEs, patients with AESIs, patients with AEs leading to trial discontinuation, and patients with other significant AEs (as described previously) and User-defined Adverse Event Concepts (UDAEC) per SSAP (cf. Table 7.8.1: 1). AEs will also be summarized by maximum intensity.

For disclosure of AE data on ClinicalTrials.gov, the frequency of patients with non-serious AEs occurring with an incidence of greater than 5 % (in preferred terms) will be summarised by treatment, primary system organ class and preferred term. The frequency of patients with SAEs will also be summarised.

For disclosure of AE data in the EudraCT register, the frequency of non-serious AEs with an incidence of greater than 5 % (in preferred terms) and the frequency of SAEs will be summarised.

7.8.2 Laboratory data

The analyses of laboratory data will be descriptive in nature and will be based on BI standards (8). Note that data from the central Laboratory will be used for all displays described below, unless otherwise specified.

For continuous safety laboratory parameters, normalized values will be derived. Normalisation means transformation to a standard unit and to a standard reference range. The process of normalisation, handling of repeat values at the same visit for by-visit displays, as well as standard analyses for safety laboratory data are described in the BI guidance for the Display and Analysis of Laboratory Data (8). All analyses considering multiple times of the ULN (as described below) will be based on standardized and not normalized values. For continuous safety laboratory parameters, differences to baseline will be calculated.

Only patients with at least one available post-baseline value will be included in the analysis of an individual laboratory parameter. All individual laboratory data will be listed. Values outside the reference range will be flagged.

Descriptive statistics of laboratory values over time and for the difference from baseline (see Section 6.7) will be based upon normalized values and provided by visit(including follow up), including summaries of the last value on treatment, the minimum value on treatment and maximum value on treatment. Graphical displays via box plots will be produced to present each continuous laboratory endpoint over time.

Laboratory values will be compared to their reference ranges; shift tables will be provided for the number of patients with a specific RCTC grade at baseline versus the grade at the last

measurement on treatment, as well as the worst grade on treatment. These analyses will be based on normalized laboratory values.

Potentially clinically significant abnormalities will be identified based on BI standard rules which are based on normalized converted lab values, i.e. using SI units. These rules will be listed in the SDL appendix of the CTR. Frequency tables will summarize the number of patients with potentially clinically significant abnormalities. Patients having an abnormal lab value at baseline will be presented separately. A separate listing will present potentially clinically significant abnormal lab group all patient's lab values will be listed, if there exists at least one lab value with clinically significant abnormality within the group.

The frequency of patients with AST or ALT elevations $\geq 3xULN$, $\geq 5xULN$, $\geq 10xULN$, and $\geq 20xULN$ will be displayed based on standardized laboratory values. To support analyses of liver related adverse drug effects, the frequency of patients with AST and/or ALT $\geq 3xULN$ combined with a total bilirubin $\geq 2xULN$ in a 30 day period after AST/ALT elevation will be displayed, stratified by alkaline phosphatase < 2xULN and $\geq 2xULN$ (a patient can potentially be in both alkaline phosphatase strata in case of multiple AST/ALT and bilirubin elevations). The start of the 30 day time span is triggered by each liver enzyme elevation above the defined thresholds. This analysis will be based on standardized laboratory values.

A graphical analysis of the ALT and total bilirubin during the on-treatment period will also be performed; the so called eDISH plot. In the graph, for each subject, the peak total bilirubin is presented as a fold increase over the ULN against the peak ALT as a fold increase over the ULN, on a log10 scale. The measurements displayed for total bilirubin and ALT may, or may not, occur on the same date. Two reference lines, 2xULN for total bilirubin and 3xULN for ALT, are drawn onto the graph in order to divide the plane into four quadrants. Normal cases are in the lower left quadrant, potential DILI cases are in the upper right quadrant (Hy's Law quadrant), while the lower right quadrant is known as the Temple's corollary range (ALT \geq 3xULN and total bilirubin < 2xULN).

Clinically relevant findings in laboratory data will be reported as baseline conditions (at screening) or as AEs (during the trial) if judged clinically relevant by the investigator, and will be analyzed as such.

